## 1. PROTOCOL SYNOPSIS

CLP 10023.B Protocol Synopsis	
Registry Title:	SMART – A prospective, multicenter registry assessing the embolization of neurovascular lesions using the Penumbra SMART COIL® System
Objective:	The primary objective of this registry is to gather post market data on the Penumbra SMART COIL® System (Smart System) in the treatment of intracranial aneurysms and other malformations.
Registry Design:	This is a prospective, multi-center registry of patients treated in accordance with the cleared indications for Smart, Penumbra Coil 400™ (PC 400), and Penumbra Occlusion Device (POD®). Data for each patient are collected in accordance with the standard of care at each participating hospital through one-year follow-up.
Patient Population:	Approximately 1,000 patients with intracranial aneurysms or other malformations treated by Smart at up to 100 centers will be enrolled.
Sample Size Justification:	Approximately 1,000 patients will be enrolled in this post market registry. Assuming an observed rate of 8.3% for the primary endpoint of re-treatment at follow-up, the sample size precision is $\pm 2\%$ for this endpoint. Assuming an observed rate of 1.7% for the primary endpoint of procedural device-related serious adverse events at immediate post-procedure, the sample size precision is $\pm 1\%$ for this endpoint. These precision estimates are based on binomial 95% confidence intervals. The sample size provides an adequate level of precision for these primary endpoints.
Inclusion Criteria:	Patients enrolled in this registry must sign the Informed Consent Form and be treated according to the cleared indications for Smart, PC 400, and POD, which include the embolization of: 
 
1. Intracranial aneurysms
 
2. Other neurovascular abnormalities such as arteriovenous malformations and arteriovenous fistulae
 

Exclusion Criteria:	
 
1. Life expectancy less than one year
 
2. Smart, PC 400, or POD account for less than 75% of total number of coils implanted
 
3. Patient previously enrolled in the SMART Registry
 
4. Participation in another clinical investigation that could confound the evaluation of the registry device
 

Endpoints:	
 
1. Retreatment through follow-up
 
2. Procedural device-related serious adverse events
 
3. Ability to achieve adequate occlusion immediate post procedure
 
4. Number of times re-access with guidewire was required due to catheter kickout
 

Registry Period:	It is anticipated patient enrollment will take 3 years. All patients are to be assessed in accordance with the standard of care at each participating hospital through one year follow-up.

## 2. INTRODUCTION

Intracranial aneurysms are a significant health problem in the United States with an estimated 1% to 6% of the adult population harboring cerebral aneurysms. The annual risk of rupture of an intact intracranial aneurysm is estimated to be approximately 1.9%. If an intracranial aneurysm ruptures, blood leaks into the highly sensitive subarachnoid space around the brain, resulting in a subarachnoid hemorrhage (SAH). SAH is known to be a major risk factor for a stroke due to the irritation of the outer layer of the nearby blood vessels surrounding the brain. This condition is associated with a high rate of mortality; close to half of ruptured aneurysms result in death within six months. Patients who survived the initial SAH are at significant risk of subsequent re-rupture. Various reports indicate that if left untreated, there is a re-bleeding rate of more than 50% within the first six months from initial presentation of a SAH.

Even if an intracranial aneurysm does not rupture, it can lead to severe complications. As the aneurysm grows, it can press on nerves, put pressure on brain tissue, or interfere with other arteries or veins. Blindness, paralysis, and other morbidities often result. Thrombus can also form within the aneurysmal sac, break off, travel downstream, and cause an ischemic stroke. It has been reported that 2.2% to 23% of patients with unruptured aneurysms may eventually experience a rupture. The International Study of Unruptured Intracranial Aneurysms evaluated the natural history of 1,937 unruptured aneurysms in 1,449 patients with a mean follow-up of 8.3 years. It reported that 2.2% of these patients had a confirmed rupture during follow-up, but 66% of them were fatal. Juvela et al. reported on the long term natural history of unruptured intracranial aneurysms in a series of 142 patients. With a median follow-up of 19.7 years, 23% of the patients experienced a SAH, which corresponds to an annualized rate of 1.3%. The cumulative rate of SAH tended to increase with time, with a rupture rate of 10.5% at 10 years, 23% at 20 years, and 30.3% at 30 years after diagnosis. Approximately half of the SAH patients did not survive. Thus, regardless of the rate of occurrence, fatality associated with this event is high in this cohort.

Prior to 1995, the traditional treatment for intracranial aneurysms was surgical clipping, in which the skull is surgically opened so metal clips can be applied to the aneurysm's neck to occlude it from the parent artery to prevent a rupture. This treatment, while effective, is high risk, highly invasive, requires an extended hospital convalescence, and is technically difficult to perform in certain regions of the brain (such as the posterior circulation). Thus, this treatment modality is not a viable option for a significant number of patients, particularly during the acute phase of SAH, when the presence of cerebral edema and evolving thrombi formation render aneurysm access difficult, if not impossible.

In the early 1990's, an endovascular treatment technique for intracranial aneurysms was first introduced by Guido Guglielmi, who used electrolytically detachable platinum coils to pack and embolize the aneurysmal sac. The

rationale was to exclude the aneurysm from the circulation and thus reduce the risk of a rupture and SAH. The Guglielmi detachable coil (GDC) was not universally accepted at first but gained significant credibility after obtaining approval from the FDA for the intracranial aneurysm indication. Moreover, a few well-conducted, prospective, randomized studies of both ruptured and unruptured aneurysms have demonstrated that angiographic and clinical outcomes from this treatment modality were equivalent, if not better, than those obtained from surgical clipping. Results were found to be similar for both treatments regardless of the inter-study differences in definitions for these outcome measures. The most important landmark study was the International Subarachnoid Aneurysm Trial (ISAT) in which a total of 2,143 patients with ruptured intracranial aneurysms were randomized to either neurosurgical clipping or endovascular GDC coiling. The results showed that at one year follow-up, 30.6% of the patients treated by neurological clipping were either functionally dependent or dead as vs. 23.7% of those treated by GDC coiling, which resulted in a risk reduction rate of 22.6%. And thus, embolic coiling has now become the standard of care worldwide for endovascular occlusion for both incidental and ruptured intracranial aneurysms.

In light of the natural history of the disease, the primary focus for management of an intracranial aneurysm must be to prevent its rupture and sequelae.

The Penumbra SMART COIL® System (Smart System), a new generation of detachable coils, is the latest in Penumbra's line of embolization tools. It has recently received 510k clearance in the U.S. and CE Mark in Europe. This coil system is specifically designed to promote aneurysm embolization.

Coil technology has evolved considerably since the initial introduction of the GDC coil over 25 years ago. In recent history, coil development has mostly focused on the delivery system, or pusher technology, and detachment. The new Smart System not only addresses improvements in the delivery system, but importantly incorporates new technology into the actual coil implant itself. Smart technology enables an individual coil to become progressively softer as it is deployed, utilizes advanced materials to improve stretch resistance, and incorporates new processes to create accurate complex and helical shapes.

Current coils available to physicians have three principal levels of softness, standard, soft and extra soft. A conventional coil currently has only one level of softness, derived from using smaller platinum filaments than a standard coil to make soft and extra soft coils. The level of softness of the Smart coils is determined not only by the diameter of the platinum filament, but also by a proprietary structural element inside the coil. This unique development enables the Penumbra Smart System to become progressively softer along the length of a single individual coil as it is being deployed. For example, deployment of a standard Smart coil begins with an atraumatic soft 2D loop, becomes standard for the body of the coil, and finishes with a soft proximal end. This progressive

softness enables the coil to be densely packed into a delicate lesion while maintaining catheter position and mitigating catheter kick-back at the end of delivery, which can preclude the successful complete embolization of the lesion.

In addition, Smart uses the latest ultra high molecular weight polymers for stretch resistance, which are 3 times stronger than current stretch resistant materials such as polypropylene (found in most 10-system coils).

The Penumbra Coil 400TM (PC400) system received 510k in the U.S. and has CE Mark.

PC400 fundamentally differs from other embolic products for treatment of brain aneurysms by offering the largest outer diameter coil available. PC400 has up to four times more volume per unit length than most other embolic coils available while still maintaining a soft and compliant feel. Together, these characteristics represent the potential to improve the ability to densely fill larger aneurysms and other neurovascular abnormalities such as arteriovenous malformations and arteriovenous fistulae, thus triggering the healing process.

Penumbra Occlusion Device (POD®), was developed to address a specific clinical need to rapidly and precisely occlude a target vessel. Current options for vessel occlusion are limited. Coils designed for aneurysms are not ideally suited for vessel embolization due to their tendency to migrate with antegrade flow. Other options, such as vascular plug technology for larger vessels, require access with large diagnostic catheters or even larger bore sheaths.

POD utilizes technology that delivers both variable sizing and softness to provide a solution for rapid and precise embolization of the target vessel.

The technology achieves this range of features through the design of a distal anchoring segment, thereby immediately anchoring the device in a range of vessel diameters. The proximal segment of the POD achieves dense occlusion by packing a softer, smaller diameter segment tightly behind the anchored portion.

All three systems (Smart, PC 400, and POD) above consist of: an implantable Coil constructed of 92% Platinum and 8% Tungsten round wire, an attached detachment pusher, and a detachment handle (packaged separately). The detachment pusher is comprised of a shaft with a radiopaque positioning marker, a distal detachment tip, and a pull wire. The detachment handle is used to detach the coil implant from the detachment pusher. All three systems are designed for endovascular embolization of aneurysms and other neurovascular abnormalities such as arteriovenous malformations and arteriovenous fistulae. The intended users for this device are physicians who have received appropriate training in interventional neuroradiology.

These devices provide a comprehensive product family for the management of intracranial aneurysms and other neurovascular abnormalities such as arteriovenous malformations and arteriovenous fistulae.

### **3. REGISTRY OVERVIEW**

This is the first multicenter post market registry examining Smart and its primary objective is to gather real world experience and data on the Smart System in the treatment of intracranial aneurysms and other neurovascular abnormalities such as arteriovenous malformations and arteriovenous fistulae.

#### **3.1 Registry Design**

This is a prospective, multi-center registry of patients treated in accordance with the cleared indications for the Penumbra Smart System, Penumbra Coil 400™ (PC 400), and Penumbra Occlusion Device (POD®) for intracranial aneurysms and other neurovascular abnormalities. Data for each patient are collected in accordance with the standard of care at each participating hospital through one-year follow-up.

#### **3.2 Registry Objectives/Endpoints**

This is the first multicenter post market registry examining the Penumbra Smart System. Its purpose is to gather real world experience on the Smart System in the treatment of intracranial aneurysms and other neurovascular abnormalities such as arteriovenous malformations and arteriovenous fistulae.

Approximately 1,000 patients with intracranial aneurysms or other malformations treated by the Penumbra Smart System, PC 400, and/or POD at up to 100 centers will be enrolled.

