### SCHEDULE OF ASSESSMENTS

Assessment	Admission Evaluation	Immediate Post-Procedure	Discharge	One Year Follow-Up*
History	√			
Modified Rankin Scale**	√			√
Hunt and Hess +	√			
Aneurysm Occlusion		√		√
Procedural Data Points ++		√		
Adverse Events		√	√	√

\* Single follow-up visit to be conducted in accordance to the standard of care at the participating hospital. Period for which to capture follow-up visit is within one year  $\pm 6$  months

\*\* Only for patients in which mRS would be captured as standard of care

+ Required for patients with SAH only

++ Proportion of SMART coils implanted, target location access attempts, radiation exposure, coiling start/end time

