## 1 Overview

SMART is a multicenter, single-arm prospective registry. Its primary objective is to acquire postmarket data on the use of the Penumbra SMART COIL® System (Smart) in the treatment of intracranial aneurysms and other malformations.

Approximately 1,000 subjects with intracranial aneurysms or other malformations treated by Smart will be enrolled across up to 100 sites. All subjects will be allocated to treatment with at least 75% Smart, Penumbra Coil 400™ (PC 400), or Penumbra Occlusion Device (POD®) coils as defined by the number of coils implanted.

The primary efficacy endpoint is the rate of retreatment through one year  $\pm$  6 months follow-up. The primary safety endpoint is the rate of procedural (within 24 hours of arterial puncture) device-related serious adverse events.

The secondary efficacy endpoints for the registry are the ability to achieve adequate occlusion at immediate post-procedure (Class I or II Raymond-Roy Occlusion Classification for aneurysms) and the number of times re-access with guidewire was required due to catheter kickout while using SMART/POD/PC 400.

This Statistical Analysis Plan (SAP) elaborates on statistical methods outlined in the registry protocol and presents analysis conventions. The SAP will be signed off before database lock.

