## 4 Analysis Populations

### 4.1 Definitions

The ITT population will consist of all subjects who sign the informed consent and are enrolled in the registry with Smart, PC 400, or POD accounting for 75% or more of the total number of coils implanted. The ITT population will include only the first lesion treated for each subject. Summary statistics will be developed separately for additional lesions.

The PP population will be constructed by excluding subjects who have major protocol violations that impact endpoint evaluations. Subjects will be classified as screen failures if they are not consented or are consented and not enrolled due to failure to implant at least 75% Smart, PC 400, or POD coils or other reasons.

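### The objective names Smart, but the planned rates describe Smart, PC 400 and POD together, and no planned output shows the coil mix or separates Smart

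*Protocol*

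**What the plan says.** **Objective.** Protocol 3.2 says of the registry: "Its purpose is to gather real world experience on the Smart System in the treatment of intracranial aneurysms". The synopsis, Protocol 3 and SAP 1 also name only the Smart System.

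**Who is enrolled.** The documents give two descriptions. The synopsis refers to "patients with intracranial aneurysms or other malformations treated by Smart at up to 100 centers will be enrolled", and SAP 1 to subjects "with intracranial aneurysms or other malformations treated by Smart will be enrolled across up to 100 sites". Protocol 3.2 instead enrols patients "treated by the Penumbra Smart System, PC 400, and/or POD at up to 100 centers will be enrolled". In SAP 1, the very next sentence applies a 75% rule to the three devices jointly.

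**Who is analysed.** SAP 4.1 defines the ITT population as consented, enrolled subjects with "Smart, PC 400, or POD accounting for 75% or more of the total number of coils implanted". Protocol 3.3.2 excludes on the same joint count. The per-protocol set removes major violations only, and the mock deviation tables have no code for absence of Smart coils.

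**What is collected.** A footnote to the protocol's Schedule of Assessments lists the procedural data points: "Proportion of SMART coils implanted, target location access attempts, radiation exposure, coiling start/end time". No SAP section, mock table or mock listing uses the first of these.

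**The concern.** A subject implanted only with PC 400 or only with POD meets every written criterion and counts fully toward all four endpoints. Yet the objective, the synopsis and SAP 1 lead a reader to expect results for Smart.

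The protocol's own Introduction gives reasons why the devices might perform differently. It presents PC 400 as a larger-diameter coil for densely filling larger aneurysms, and POD as a device built to occlude a vessel. It credits Smart's progressive softness with reducing catheter kick-back. Kickout is an endpoint, but SAP 8.2 counts it over all three devices, so the planned output cannot isolate the feature claimed for Smart.

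At stake is what the final report can say. Without a coil-mix table, a reader cannot tell whether the pooled rates are close to Smart rates or some distance from them.

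**Working it through.** **Text check.** I looked for any place where Smart is separated from the other two devices.

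- Entry rule and ITT set (Protocol 3.3.2, SAP 4.1): joint 75% count, so the Smart share may be 0%.
- Subgroups (SAP 9): nine variables (adjunctive treatment, age, aneurysm location, size and status, lesion nature, technique, neck width, treatment at admission). Coil type is not among them.
- Kickout (SAP 8.2 and its mock table): the three devices together, split only from other adjunctive coils.
- Mock tables and listings: none shows coil mix.
- Device-relatedness: the listings share one column heading for the three devices. The number of grading sets under that heading differs between listings (three in the SAE listing, two in the listings of related events), and the tables are broken in the text. Whether relatedness is graded per device cannot be settled.

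**Reproducing the plan's precision.** Inputs from SAP 2: n = 1,000, 8.3% retreatment, 1.7% SAE, normal approximation. Half-width h = 1.96 × √(p(1 − p)/n).

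- Retreatment: 1.96 × √(0.083 × 0.917/1000) = 1.71 points, giving 6.59% to 10.01%. This matches the stated 6.6% to 10.0%.
- SAE: 1.96 × √(0.017 × 0.983/1000) = 0.80 points, giving 0.90% to 2.50%. The upper limit matches. The stated lower limit is 0.93%, a small discrepancy that does not bear on this point.

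**How far pooling could move the rate.** The documents give neither the share of non-Smart subjects (s) nor device-specific rates, so both are assumed. For simplicity each subject is treated as either Smart or other. With Smart at 8.3% and the other devices at r times that, the pooled rate is 8.3% × (1 − s + s·r).

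| Non-Smart share s | Others at half (r = 0.5) | Others at double (r = 2) |
|---|---|---|
| 5% | 8.1% (−0.2) | 8.7% (+0.4) |
| 10% | 7.9% (−0.4) | 9.1% (+0.8) |
| 20% | 7.5% (−0.8) | 10.0% (+1.7) |
| 30% | 7.1% (−1.2) | 10.8% (+2.5) |

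For the SAE endpoint, the same formula with 1.7% and s = 20% gives 1.53% to 2.04%, a shift of −0.17 to +0.34 points against the 0.80 half-width.

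**Precision in a Smart-defined subset.** At 8.3%, n = 750 gives 1.96 × √(0.083 × 0.917/750) = 1.97 points, and n = 500 gives 2.42. The smallest n that keeps the stated ±2 points is 1.96² × 0.083 × 0.917/0.02², or 731. For ±1 point at 1.7% it is 1.96² × 0.017 × 0.983/0.01², or 642. So about 73% of 1,000 subjects would have to qualify and have an observed retreatment outcome.

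**The case against.** The three-device scope is not hidden. It stands in the synopsis rows on design, inclusion and exclusion, in Protocol 3.1 to 3.3, in SAP 1 and in SAP 4.1, and the kickout table carries the family label. The Introduction also gives a rationale for pooling: the three systems share the same alloy and detachment design, serve the same indications and are presented as one product family. The objective is descriptive, with no hypothesis, comparator or performance goal, so nowhere do the documents promise a rate attributable to Smart. Device choice follows the lesion, so a split by device would be confounded. SAP 9 already stratifies by aneurysm size, lesion nature and technique. The recorded Smart proportion is undefined and might mean the family share needed for the entry rule.

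Most of this stands, and it limits the point. A reader might infer that the registry cannot meet its objective, or that its rates will be wrong for Smart. The documents support neither reading: gathering descriptive post-market data is compatible with a family-level result, and if nearly all subjects receive mainly Smart coils the pooled and Smart rates will be close. Confounding argues against comparing devices, but not against describing the Smart-treated subjects. The existing subgroups are at best proxies for device. What remains is that the documents describe the enrolled population in two ways and that no output lets a reader see how much of the result is Smart.

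**Conclusion.** The point holds as a mismatch between objective, population and outputs. As planned, the four endpoint rates are device-family rates and should not be reported as Smart rates.

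The size of any distortion cannot be determined from the documents. Over the assumed range it runs from negligible (at most about 0.4 points with a 5% non-Smart share) to about the planned half-width (+1.7 points with a 20% share at double the rate). These figures rest on an assumed share, assumed rate ratios of 0.5 to 2, and Smart retreatment at the planning value of 8.3%, which SAP 2 takes from eight prior studies and not from any mix of these devices. They illustrate sensitivity and do not estimate bias.

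**What to change.** 1. Reconcile the population wording in the synopsis and SAP 1 with Protocol 3.2 and the 75% rule.
2. Define the recorded proportion of SMART coils as Smart-only. If it means the family, derive the Smart share from coil-level procedure records.
3. Add a coil-mix table to the mock outputs.
4. Label full-ITT results as device-family results.
5. In SAP 4.1 and 8 to 10, prespecify a descriptive analysis of the four endpoints in a Smart-defined subset. At least 75% Smart coils would mirror the entry rule, though other cut-offs are defensible. Show the remaining subjects separately and state that no causal comparison between devices is intended, because device choice follows lesion type.
6. State whether relatedness is graded per device. If it is not, the subset SAE figure is a rate among mainly-Smart subjects and cannot be attributed to Smart.

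The full-ITT analysis is unchanged. The cost is one derived variable if the Smart share is already recorded (more if it must be rebuilt from procedure records), repeated tables, and a wider interval in the subset. Restating the objective as the three-device family would also remove the mismatch, but would leave nothing reported on Smart itself.
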